### 9.7.5. Exploratory outcome analyses

### 9.7.5.1. All-cause mortality

The analysis of all-cause mortality will be estimated in the overall study cohort without any outcome-specific exclusion criteria. Because there are no competing risks for mortality, weighted treatment group–specific Kaplan-Meier survival plots and overall HR will be estimated without accounting for competing risks.

### 9.7.5.2. Change in UACR values over time

The analysis of change in UACR values over time will be performed in an analysis set restricted to those with available baseline UACR values (Section 9.3.3.2.4). Recorded UACR values during follow-up will be identified and used to estimate change in UACR values from baseline at 4 months and 12 months after the Time 0 with pattern-mixture models [61]. The factors considered as censoring criteria for the other, time-to-event outcomes will be used to define loss-to-follow-up for these analyses.

Descriptive analyses of UACR over time at 4 months and 12 months will be performed in each treatment group. Comparisons between groups may be considered, if feasible, based on descriptive analyses of UACR testing frequency between treatment groups (Section 9.7.4.3; further details to be provided in the SAP).

#### 9.7.6. Subgroup analyses

To evaluate whether the association of finerenone with outcomes of interest differs by clinically relevant subgroups, HRs and 95% CIs across all of follow-up will be estimated in the following subgroups, if feasible due to observed case counts:

- Age groups
- Sex
- SGLT2i use at Time 0
- ACEi/ARB use at Time 0
- GLP-1 RA use at Time 0
- Insulin use at Time 0
- Potassium-sparing diuretic use at Time 0 (for hyperkalaemia only)
- UACR level at Time 0
- eGFR stage at Time 0
- Previous AMI at Time 0 (for AMI only)

As noted, some subgroup analyses will be performed specifically for only select, relevant outcomes.

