#### 9.2.1.2. Selection criteria

Individuals must meet all the following inclusion criteria on or before Time 0 to be included in the cohort:

- Active registration or continuous enrolment for at least 365 days in the data source before Time 0 (days [-365, 0])
- No recorded use of finerenone before Time 0 (days [-all available, 0])
- Aged 18 years or older on Time 0
- Diagnosis of T2D at any time on or before Time 0 (days [-all available, 0])
- Evidence of CKD on or before Time 0 (days [-all available, 0]), identified by meeting any of the following criteria:
  - A diagnosis code indicating CKD stage 1, 2, 3, 4, or stage unspecified
  - Two UACR test results  $\geq$  30 mg/g separated by at least 90 days and no more than 540 days.
  - Two different eGFR test results  $\geq 15 \text{ mL/min}/1.73 \text{ m}^2 \text{ AND}$ < 90 mL/min/1.73 m^2 [17] separated by at least 90 days and no more than 540 days. If a reported eGFR test result is available in the data, it will be used as recorded to determine eligibility (as that was the eGFR value available to the prescribing clinician at the time of Time 0). If an eGFR value is not reported, but there is sufficient information to calculate the eGFR, it will be calculated using the creatinine-based 2021 CKD-EPI equation [18] (Section 9.3.1).

Individuals will be excluded if they meet any of the following exclusion criteria on or before Time 0:

- Type 1 diabetes (T1D) at any time on or before Time 0 (days [all available, 0]), as finerenone is not indicated for use in T1D
- Evidence of end-stage kidney disease (ESKD) at any time on or before Time 0 (days [all available, 0]) —as finerenone is not recommended to be initiated in individuals with ESKD or severely reduced eGFR—identified as any of the following criteria:
  - Two different eGFR test results < 15 mL/min/1.73 m^2 [17] separated by at least 90 days and no more than 540 days
  - Dependence on dialysis (at least 3 sessions over at least 90 days)
  - A diagnosis code indicating kidney failure or CKD stage 5 (International Classification of Diseases, 10th Revision, Clinical Modification [ICD-10-CM] code N18.5)
  - A diagnosis code indicating having a kidney transplant (ICD-10-CM code Z94.0)
- Diagnosis of kidney cancer at any time on or before Time 0 (days [-all available, 0]), as decreased renal function resulting from kidney cancer may differ in treatment response from diabetic CKD.

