#### 9.3.3.1. Primary composite cardiovascular outcome

The primary composite cardiovascular outcome will evaluate the first occurrence of any of the following events during follow-up:

- An inpatient hospital diagnosis of fatal or nonfatal acute myocardial infarction [29]
- An inpatient hospitalisation with a primary diagnosis of heart failure [30]

Individuals with prior cardiovascular events are eligible for finerenone treatment; thus, those with an occurrence of these events before Time 0 may be included in the overall study cohort (before application of outcome-specific exclusion criteria). However, to ensure identification of cardiovascular outcomes that newly occur after Time 0, analysis of this composite cardiovascular outcome will be performed in an analysis set that also excludes individuals with an acute myocardial infarction diagnosis in the 365 days before Time 0. Those with a history of heart failure will be included in the analysis, and history of heart failure will be included.

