### 9.3.3.2.1. Acute myocardial infarction

Finerenone is indicated in the US for the prevention of cardiovascular death and nonfatal acute myocardial infarction (AMI), among other events [13]. The AMI outcome will identify the first occurrence of an inpatient hospital diagnosis of fatal or nonfatal AMI [29] during follow-up. To ensure that AMI events identified during follow-up represent new events rather than continuing care for previous events occurring before Time 0, the analysis of this outcome will be performed in the same analysis set as the primary composite outcome, which also excludes individuals with an AMI diagnosis in the 365 days before Time 0.

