### 9.3.3.2.3. New-onset heart failure

The US indication for finerenone includes the prevention of hospitalisation for heart failure, and the secondary hospitalisation for heart failure outcome (Section 9.3.3.2.2) will include individuals with a history of heart failure before Time 0. A secondary outcome will further evaluate new diagnoses of heart failure among individuals without a history of heart failure. The secondary new-onset heart failure outcome will evaluate the first occurrence of an inpatient hospital or emergency department diagnosis of heart failure [30] during follow-up. To ensure identification of new-onset heart failure, analysis of this outcome will be performed in an analysis set that also excludes individuals with a diagnosis of heart failure at any point before Time 0.

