#### 9.3.4. Covariate definitions

Covariates include risk factors for renal progression [39,40], cardiovascular outcomes [41,42], or hyperkalaemia [43-45]. Variables potentially associated with the use or non-use of finerenone and the outcomes of interest—e.g., concomitant medications, comorbidities—will be identified for all cohort members before or on Time 0 using diagnosis, procedure, or medication information available in the data source. A detailed description of definitions and code lists for all covariates that will be used in the data source will be specified in the SAP. Covariates will be defined using ICD-10-CM diagnosis codes, laboratory records, procedure coding, or medication coding, as appropriate for each variable.

The following demographic characteristics will be evaluated as of Time 0:

- Age
- Sex
- Calendar year of Time 0
- Race and/or ethnicity (as available in the data)
- Socioeconomic status (as available in the data)
- US geographic region
- Insurance plan type

The following clinical characteristics of patients will be defined using the 365 days before and including Time 0, except where specified otherwise:

- Markers of T2D severity (as available in the data source) and components of the Diabetes Severity Complications Index [46,47] not listed elsewhere
  - Duration of T2D (in all available lookback, as available in the data source)
  - Insulin use
  - Haemoglobin A1c (glycated haemoglobin) (HbA1c) (most recent recorded laboratory value in the 183 days before and closest to Time 0, if available)
  - Hyperosmolar hyperglycaemic state
  - Ketoacidosis

- Lower limb amputations (all available lookback, as available in the data source)
- Neuropathy
- Retinopathy
- Markers of kidney dysfunction severity
  - Duration of CKD (all available lookback, as available in the data source)
  - CKD stage, defined based on eGFR, or stage-specific diagnosis codes (using all available lookback) (Section 9.3.1)
  - Albuminuria stage defined based on UACR values (Section 9.3.1)
  - Proteinuria, defined based on diagnosis codes (Section 9.3.1)
  - Nephrotic syndrome, based on diagnosis codes (Section 9.3.1)
  - Glomerulonephritis
  - Renovascular disease
  - Polycystic kidney disease
  - Autoimmune disease
  - Gout/hyperuricaemia
  - Hospitalisation episodes for acute kidney injury

The following comorbidities will be defined using all available lookback before and including Time 0:

- Cardiovascular comorbidities
  - Acute myocardial infarction

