#### 9.9. Limitations of the research methods

This study will use existing healthcare data. As with all studies based in existing healthcare data sources, the data are generated for healthcare delivery rather than research; thus, missing data or misclassification of study variables is possible.

Written prescription or dispensing data may not reflect actual exposure or nonexposure to finerenone. A prescription issued or a prescription dispensed reflects the intent to use a drug, not actual patient use. Dosage, duration of use, and treatment changes will be estimated from the data; however, not all patient behaviours may be accurately recorded in the data, resulting in potential misclassification of finerenone use, discontinuation date, or dosage.

CKD will be defined using laboratory values (where available) and diagnosis coding. This approach may introduce heterogeneity in the evaluation of CKD severity across study participants. Additionally, formulas for estimating eGFR may vary across time, geographies, and racial and/or ethnic groups. This study will use a standard single equation, CKD-EPI 2021, to estimate eGFR where possible. However, in the absence of complete laboratory records, diagnosis coding will be used, which may lack the granularity of laboratory-based measures.

Cohort entry is defined by meeting electronic algorithms for both T2D and CKD using data available in the data source during the study period. Thus, the original dates of CKD and T2D onset may not be known for each individual. Additional measures of T2D and CKD disease severity will be included as covariates, but duration of illness cannot be considered.

Moreover, specific ordering of the onset of CKD and T2D will not be required. Individuals with T2D who develop CKD may have different treatment patterns and characteristics than those with CKD who develop T2D, but both groups will be included in the present study.

Outcomes will be identified using all relevant diagnosis information using validated algorithms, where available; however, misclassification is possible.

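### The 365-day AMI washout equals the 365-day minimum enrolment, so the previous-AMI subgroup partly sorts records by how much data they have

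*Protocol*

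**What the plan says.** All references are to the protocol.

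- **Entry (9.2.1.2):** "Active registration or continuous enrolment for at least 365 days in the data source before Time 0".
- **Washout (9.3.3.1 and 9.3.3.2.1):** the primary composite set "excludes individuals with an acute myocardial infarction diagnosis in the 365 days before Time 0". The AMI outcome is analysed in that same set, "which also excludes individuals with an AMI diagnosis in the 365 days before Time 0".
- **Subgroup (9.7.6):** within that set, estimates are planned by "Previous AMI at Time 0 (for AMI only"). The only condition attached is that case counts allow it.
- **Source of history (9.3.4):** "The following comorbidities will be defined using all available lookback before and including Time 0". The list includes AMI and congestive heart failure. Code lists are left to the SAP.
- **Reach of the data (9.2.2):** cohort entry starts on 09 July 2021. Earlier data may be used, possibly back to 01 October 2015 where available.
- **Absent records (9.10.2):** for variables defined by the presence of a record, no record means the condition is taken as absent.
- **New-onset heart failure (9.3.3.2.3):** the analysis set "excludes individuals with a diagnosis of heart failure at any point before Time 0".
- **Duration of disease:** 9.3.4 lists duration of T2D and duration of CKD as covariates, measured over all available lookback. Section 9.9 says: "Additional measures of T2D and CKD disease severity will be included as covariates, but duration of illness cannot be considered".

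**The concern.** The washout and the entry minimum have the same length and cover the same days. In a record with only the minimum data, an AMI in the visible year excludes the patient, and an older AMI lies outside the data. Under the absent-record rule, the patient is then counted as never having had an AMI.

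The two strata therefore differ in more than cardiac history. The previous-AMI stratum can hold only records with more than 365 days of data, apart from the small exceptions noted below. The other stratum mixes patients truly without a previous AMI with patients whose AMI predates their data. A difference in hazard ratio between the strata, or the absence of one, could not be read cleanly as effect modification by AMI history.

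The new-onset heart failure set raises a milder version of the question. A criterion covering any time before Time 0 can mean one year of screening in one patient and several years in another.

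**Working it through.** **Inputs.** Minimum enrolment 365 days (9.2.1.2); AMI washout 365 days (9.3.3.1, 9.3.3.2.1); earliest possible data 01 October 2015 and cohort start 09 July 2021 (9.2.2). Let L be the days of data available before a given Time 0.

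**Step 1: window for a previous AMI.** To be classed as previous AMI and remain in the analysis set, the AMI must be recorded in the data but before the washout. The usable window is

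W = max(0, L − 365).

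| L (days) | W (days) |
|---|---|
| 365 | 0 |
| 366 | 1 |
| 548 | 183 |
| 730 | 365 |
| 1,095 | 730 |
| 2,108 | 1,743 |

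The last row is the longest possible lookback for a Time 0 on the first day of cohort entry: 01 October 2015 to 09 July 2021 is 2,108 days, and 2,108 − 365 = 1,743.

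**Step 2: classification.** When W = 0, no AMI event before Time 0 can place the record in the previous-AMI stratum, so 9.10.2 sends it to the other one. When W is small, only an AMI in a short band of time can be seen. There are two exceptions. An AMI coded on day 0 counts as history, because the 9.3.4 lookback includes Time 0. An old-infarction code recorded during the washout year could reveal an earlier event, but only if the SAP accepts it for history and leaves it out of the washout list. If one list serves both purposes, that patient is excluded.

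**Step 3: new-onset heart failure.** No washout cancels the lookback here. A heart failure diagnosis in the last year always leads to exclusion, as does any older diagnosis in the data, so only disease recorded solely before the data begin is missed. To see whether the size can be pinned down, let h be the true prevalence of earlier heart failure, s the sensitivity of the available lookback, and r the event rate ratio of prior to no prior disease. None of these is in the protocol. Then

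share of the set = h(1 − s) / [h(1 − s) + (1 − h)]

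share of events = h(1 − s)r / [h(1 − s)r + (1 − h)].

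- Low end (h = 10%, s = 99%, r = 2): share of the set 0.001/0.901 = 0.1%; share of events 0.002/0.902 = 0.2%.
- High end (h = 30%, s = 80%, r = 10): share of the set 0.06/0.76 = 8%; share of events 0.6/1.3 = 46%.

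A range of 0.2% to 46% shows that the size depends almost entirely on the assumptions.

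**The case against.** The strongest reply is that 365 days is a floor, while history is taken from all available data. That data may start before the qualifying enrolment spell and may include medical records as well as claims (9.4). The protocol gives no distribution of lookback, so few records may sit at or near the floor. This stands: zero sensitivity for previous AMI describes the boundary, not the whole subgroup.

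A second reply is that the SAP's code lists may solve the problem. They could, but only with different lists for washout and history, which the protocol does not state.

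A third is that shared under-recording mainly blurs the contrast between strata and does not bias finerenone against non-use. This also stands as far as the documents go. A person's finerenone Time 0 does fall after that person's own comparator Time 0s (9.2.1.1), but the direction across the whole groups is unknown. Calendar year and the two duration covariates would partly track lookback in the propensity model, and 9.7.2 allows covariates to be added.

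A reader might go further and infer that new-onset heart failure will contain a material share of known disease, perhaps 4% to 33% of events. Those figures follow from assuming 15–25% prevalence, 5–15% of cases missed in one year and a 5- to 10-fold rate ratio, and from applying the one-year miss rate to every patient. The documents support none of these inputs, and many patients may have longer lookback.

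**Conclusion.** The AMI point holds on the protocol's own windows. At the minimum lookback the previous-AMI stratum is closed to the patient, and just above the minimum it is nearly closed, so stratum membership depends partly on length of data. This assumes that the SAP does not use separate history codes. The number of affected records is unknown.

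For new-onset heart failure the flaw is not structural. Some prior disease may be missed, to a degree that varies between patients and that the documents do not allow to be calculated.

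The consequence is confined to one subgroup analysis and, more weakly, one secondary outcome. The primary composite is touched only through AMI and other history used as covariates, and no imbalance in lookback between treatment groups has been shown. A change is still worthwhile because it is cheap and makes the strata mean what their label says.

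The conflict between 9.3.4 and 9.9 on duration of illness is a separate matter of wording and adds no weight to the point above.

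**What to change.** 1. Run the previous-AMI subgroup analysis only in Time 0s with a minimum lookback clearly longer than the washout. Values of 730 or 1,095 days are examples; choose from the observed lookback distribution before outcomes are examined. Apply the restriction to both strata and define the subgroup as AMI more than 365 days before Time 0.
2. Add a sensitivity analysis of new-onset heart failure under the same longer-lookback restriction.
3. Report lookback length by treatment group, and consider it for the propensity model if it is imbalanced. Name variable lookback as a limitation in 9.9.
4. Separately, reconcile the duration of T2D and CKD covariates in 9.3.4 with the statement in 9.9.

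The cost is one derived variable and one filter on existing data, with fewer records in the AMI subgroup and in the heart failure sensitivity analysis. The primary analysis loses no records.

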#### 9.7.7. Sensitivity analyses

#### 9.7.7.1. Negative control analysis

To evaluate the potential for unmeasured confounding and other residual bias, a negative control outcome analysis will be performed. Negative control outcomes should not be causally related to the exposure, but as much as possible, should have the same set of common causes as the study exposure-outcome association being evaluated [62]. The outcomes being evaluated (cardiovascular and kidney outcomes) may also be influenced by other behavioural factors that are difficult to measure in existing healthcare data, such as diet, exercise, or other lifestyle factors; healthcare-seeking behaviour; or adherence to medications. Thus, potential negative control outcomes to assess the impact of unmeasured confounding by these factors would also require some association with healthy lifestyle.

A negative control outcome will be selected using the following criteria:

- The outcome should not be caused by finerenone use, directly or indirectly; thus, any outcomes with known associations, signals detected in pharmacovigilance systems, or published case reports will not be considered.
- The outcome should be severe (requiring hospitalisation or emergency department admission) to match the severity of the primary outcomes.
- The outcome should be reasonably common, matching the expected incidence of the outcomes of interest in this population.

Initially considered negative control outcomes may include the following:

- Hospitalisation or emergency department visit for asthma
- Laceration of hand or finger

### 9.7.8. Secondary treatment strategy analysis

A secondary analysis will evaluate outcomes using an alternative treatment strategy, requiring uptitration of the daily finerenone dose to 20 mg according to the approved US label (Section 9.3.2.3). This strategy will use methods similar to those for the primary analyses, but the censoring criteria will also include deviation from the new strategy (i.e., failure to titrate by week 10). These analyses will begin with the same study population as that from the primary analysis; thus, the same propensity scores and baseline variables will be used, but new IPC weights will be calculated due to the difference in censoring criteria.

### 9.8. Quality control

Standard operating procedures or internal process guidance at the research centre(s) will be used to guide the conduct of the study. These procedures include internal quality audits, rules for secure and confidential data storage, methods to maintain and archive project documents, QC procedures for programming, standards for writing analysis plans, and requirements for senior scientific review.

All programming written by 1 study analyst will be reviewed independently by a different analyst, with oversight by a senior statistician; all QC activities will be performed and documented pursuant to RTI-HS SOPs. All key study documents, such as the SAP and study reports, will undergo QC review, senior scientific review, and editorial review.

For RTI-HS, an independent Office of Quality (OQ) may perform audits and assessments that involve various aspects of the project, including but not limited to education and training documentation, data entry and data transfer procedures and documentation, and institutional review board (IRB) documentation. Such audits will be conducted by the OQ according to established criteria in SOPs and other applicable procedures.

A quality assurance audit of this study may be conducted by the study funder or the study funder's designees.

#### 9.9. Limitations of the research methods

This study will use existing healthcare data. As with all studies based in existing healthcare data sources, the data are generated for healthcare delivery rather than research; thus, missing data or misclassification of study variables is possible.

Written prescription or dispensing data may not reflect actual exposure or nonexposure to finerenone. A prescription issued or a prescription dispensed reflects the intent to use a drug, not actual patient use. Dosage, duration of use, and treatment changes will be estimated from the data; however, not all patient behaviours may be accurately recorded in the data, resulting in potential misclassification of finerenone use, discontinuation date, or dosage.

CKD will be defined using laboratory values (where available) and diagnosis coding. This approach may introduce heterogeneity in the evaluation of CKD severity across study participants. Additionally, formulas for estimating eGFR may vary across time, geographies, and racial and/or ethnic groups. This study will use a standard single equation, CKD-EPI 2021, to estimate eGFR where possible. However, in the absence of complete laboratory records, diagnosis coding will be used, which may lack the granularity of laboratory-based measures.

Cohort entry is defined by meeting electronic algorithms for both T2D and CKD using data available in the data source during the study period. Thus, the original dates of CKD and T2D onset may not be known for each individual. Additional measures of T2D and CKD disease severity will be included as covariates, but duration of illness cannot be considered.

Moreover, specific ordering of the onset of CKD and T2D will not be required. Individuals with T2D who develop CKD may have different treatment patterns and characteristics than those with CKD who develop T2D, but both groups will be included in the present study.

Outcomes will be identified using all relevant diagnosis information using validated algorithms, where available; however, misclassification is possible.

This study will compare finerenone users with nonusers. While the study selection criteria are designed to ensure that all nonusers are eligible to be prescribed finerenone on all identified Time 0s, systematic differences in characteristics may be present between finerenone initiators and nonusers, resulting in unmeasured confounding (e.g., if finerenone users are generally at more advanced disease stages than nonusers, there may be a confounded estimate demonstrating an elevated outcome rate in treated individuals). This study uses a rich set of covariates, including demographic characteristics, comorbidities, and comedications, as well as proxies for healthcare-seeking behaviour and healthy lifestyle. The balance of measured characteristics will be evaluated, negative control outcomes will be evaluated to determine the potential impact of unmeasured confounding, and a sensitivity analysis will use restrictive inclusion criteria to create more similar treatment groups. However, the possibility of unmeasured confounding remains.

Comparisons of medication users with nonusers may be subject to selection bias if treated individuals must meet additional criteria (e.g., additional survival, healthcare interactions) to be included in the study beyond those of the comparator group criteria. For the comparator group in this study, all dates on which individuals had a recorded CKD diagnosis and were eligible for finerenone treatment will be included in the comparator group. This will include a large array of individuals with CKD at each timepoint their CKD was recognised and evaluated. However, if in practice, there are requirements for finerenone prescription that systematically require additional survival (e.g., a long evaluation period), selection bias may be present. This limitation also applies to analyses of the recommended titration schedule of finerenone. Individuals who do not follow the titration schedule will be censored, potentially introducing selection bias in follow-up. Inverse probability of censoring weights will be used to account for selection bias, but residual bias may remain if some key characteristics are not measured in the data.

To optimise internal validity, this study will assess patients who have been or who could have been prescribed finerenone according to the approved label in the US. Some of these eligibility criteria based on the approved label or treatment recommendations are intended to improve comparability of treated and untreated groups (e.g., exclusion of those with recent hyperkalaemia), thus avoiding comparison of treated individuals with untreated individuals whose clinical state makes them unlikely to be treated and more likely to experience negative outcomes. These criteria are primarily intended to impact the untreated comparison group, but they are also likely to exclude a small number of treated individuals. Consequently, this approach may impact the representativeness of the study results. The study results will be representative of patients prescribed finerenone according to the approved label in the US, but results need to be interpreted with care beyond the labelled indication of finerenone in the US.

A secondary objective of this study will assess the effectiveness of initiating finerenone and titrating dosage according to the approved label by estimating the risk of a composite cardiovascular outcome (i.e., first occurrence of fatal or nonfatal AMI or hospitalisation for heart failure) in patients with CKD and T2D initiating finerenone and uptitrating to 20 mg (when recommended) compared with that in patients with CKD and T2D not using finerenone. Patients in the finerenone group will therefore be censored if they do not seem to follow the titration recommendation from the US label. However, in the control group (no

finerenone use), no such censoring will be possible because these patients do not use finerenone.

